4. SUBJECT INFORMATION

Subject information will be analyzed on the safety set (AST) and the Intention-To-Treat-infected (ITT-i) set, unless specified otherwise for a specific display.

4.1. Demographics and Baseline Characteristics

All demographics and baseline characteristics will be summarized overall and by treatment group. Descriptive statistics and frequency distribution will be provided for respectively the continuous and categorical parameters here below.

Demographic parameters:

- Sex (Male, Female)
- Race (White, Black or African American, Asian, American Indian or Alaska Native, Native Hawaiian or Other Pacific Islander).
- Ethnicity (Hispanic or Latino, Not Hispanic or Latino)
- Country
- Geographic region (based on country: North America [to include Puerto Rico], Europe, South America, Asia-Pacific)
- Region (Japan, non-Japan) Note: Japan region only includes subjects indicated as Japanese on the CRF.
- Age (months)
- Age category [≥ 28 days to < 24 months, ≥ 24 to ≤ 36 months]
- Weight at baseline (kg)
- Weight at baseline (kg) quartiles [1st Quartile, 2nd Quartile, 3rd Quartile, 4th Quartile]
- Height at baseline (cm)
- Height at baseline (cm) quartiles [1st Quartile, 2nd Quartile, 3rd Quartile, 4th Quartile]
- BMI at baseline (kg/m^2) = Weight at baseline (kg) / (Height at baseline (m))² (rounded to 1 decimal. Even if available in the raw data, BMI will be recalculated from baseline weight and height)
- BMI at baseline (kg/m^2) quartiles [1st Quartile, 2nd Quartile, 3rd Quartile, 4th Quartile] for each of the age categories

Baseline disease characteristics:

- Duration of RSV symptoms from onset till time of randomization (days)
- Duration of RSV symptoms from onset till time of randomization (days) categories (≤ 3 days; > 3 days to ≤ 5 days)
- Presence comorbid conditions (yes, no)
- Number of subjects with one of following comorbid conditions:
 - o prematurity at birth [subject's gestational age was < 37 weeks; for infants < 1 year old at randomization],
 - o bronchopulmonary dysplasia,
 - o congenital heart disease,
 - o other congenital diseases,
 - o Down syndrome,
 - o neuromuscular impairment, or
 - o cystic fibrosis

- Baseline RSV Viral load (\log_{10} copies/mL)
- Baseline RSV Viral load [$\leq C \log_{10}$ copies/mL, $>C \log_{10}$ copies/mL] with C = rounded median
- Baseline RSV subtype
- Receiving Supplemental Oxygen (yes, no)
- Reasons for hospitalization (PRESORS question 1)

4.2. Disposition Information

Screened subjects and reason for screen failures will be summarized overall.

The number of subjects in the following disposition categories will be summarized throughout the study by treatment group and overall:

- subjects randomized, randomized and not treated, treated and not randomized, randomized or treated, safety set, intent-to-treat set, intent-to-treat-infected set and per-protocol analysis set.
- subjects who completed and discontinued treatment and the trial, with the reasons of discontinuation.
- subjects per phase and per analysis visit in the trial

4.3. Treatment Compliance

Treatment compliance will be calculated for the loading dose and maintenance dose separately. The treatment compliance will be calculated as follows:

Treatment compliance (%) = $100 \times \text{number of doses of study medication} / \text{planned number of doses according to the protocol (including additional doses needed because of treatment extension)}$

The planned number of doses is 1 loading dose and 9 maintenance doses. In case of treatment extension the maximum planned number of doses for the maintenance doses will be 19.

Treatment compliance will be summarized descriptively by treatment group.

4.4. Extent of Exposure

Descriptive statistics for treatment duration will be presented by treatment group.

The treatment duration is defined as date/time of last study drug intake – date/time of first study drug intake + 72 hours.

Note: treatment interruptions will not be taken into account for the above definition.

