It is important to note that these projections are based on predicted pediatric PK, and will continue to be revised and updated as pediatric data are collected in the ongoing Study ALS-8176-503. Given the active nature of the ongoing development program, the IDMC may recommend that dose regimens be removed or adjusted based on safety and/or viral activity considerations from ongoing studies. Irrespective of the dose, the average projected JNJ-63549109 plasma exposure (Table 3) is expected not to exceed a projected average AUC_{0-24h} of 20,000 ng.h/mL (or 25,200 ng.h/mL in whole blood), a limit that is 2.7-fold lower than the lowest systemic NOAEL observed in nonclinical toxicity studies.

The active regimens evaluated in this design will be selected to provide a range of plasma JNJ-63549109 and intracellular JNJ-63549109-nucleoside triphosphate exposures aimed at providing information on efficacy, safety, tolerability, and PK in the target population of infants and children who are aged ≥28 days to ≤36 months and who are hospitalized with RSV.

Treatment Duration

Treatment will last for 5 days as this was the duration of treatment assessed in healthy adult subjects infected with RSV in a human challenge model (Study ALS-8176-502), which demonstrated substantial declines in RSV viral load and improvement in RSV signs and symptoms (see Section 1.1). Five days is also the duration being studied in the MAD part of Study ALS-8176-503 in pediatric subjects. The long terminal t_{1/2} of the NTP is anticipated to provide therapeutic levels of the active NTP beyond the 5-day treatment duration. The treatment duration may be extended to up to 10 days if recommended by the IDMC, based on emerging data from ongoing clinical studies with lumicitabine.

Clinical Outcomes of RSV Treatment

Treatment with lumicitabine may reduce the severity and duration of RSV signs and symptoms and their impact on functioning, reduce the need for and duration of supportive care (eg, oxygen supplementation, intravenous (IV) fluids, days of hospitalization), and accelerate the subjects' return to pre-RSV health status. The study will compare treatment regimens to evaluate the impact of treatment with lumicitabine on the clinical course of RSV disease.

Pharmacokinetic Sampling Schedule

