6. DOSAGE AND ADMINISTRATION

The study drug will be provided as a powder for suspension for oral administration. Study drug administration should start as soon as possible, but no later than 4 hours after randomization in order to maximize the opportunity for the compound to inhibit viral replication and potentially improve outcomes.

Subjects will be dosed with a single LD followed by 9 MDs twice daily (minimum 8 hours and maximum 16 hours apart with no more than 2 doses per calendar day) during Day 1 to Day 5/6 (depending on the timing of the LD).

Administration of each dose should occur at approximately the same time each day and after the once-daily collection of the mid-turbinate nasal swab. Lumicitabine can be administered without regard to food. The date and time of dose administration, the date and time of food intake (limited to the food ingested within 30 minutes before or after study drug administration), and the type of food will be recorded in the eCRF for hospitalized subjects.

Lumicitabine and placebo will be supplied as a powder in amber glass bottles containing 1,891 mg lumicitabine or placebo with a child-resistant cap. The powder should be suspended with solvent prior to oral administration, providing a 60 mg/mL suspension, under the supervision of the investigator or a qualified member of the study-site personnel, or by a hospital/clinic pharmacist. Instructions for preparation of weight-based study formulations are provided in the pharmacy manual.

In case a dose is missed, the dose may be given up to 6 hours after the scheduled time. If more time has elapsed the dose should be skipped and the next dose should be given at the next scheduled timepoint per the initial dose schedule.

In case the subject is discharged prior to the completion of dosing, study drug administration will continued at home by the parent(s)/caregiver(s) until all doses are administered (Day 5/6). The investigator/study-site personnel will instruct parent(s)/caregiver(s) on how to store study drug for at-home use as indicated for this protocol (see pharmacy manual).

An overdose in this study is defined as a calculated dose exceeding the planned dose.

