2. GENERAL ANALYSIS DEFINITIONS

2.1. Visit Windows and Phase Definition

Figure 1: Schematic Study Overview: Option A

Abbreviations: LD: loading dose; MD: maintenance dose; RSV: respiratory syncytial virus.

- a. Subjects randomized to placebo will be subsequently randomized in a 1:1 ratio to the placebo regimen matching Regimen A or Regimen B.

Phases will be constructed as follows:

Trial phase	Start date	End date
Pre-screening	Date time of first assessment, taken as part of standard of care within 84 hours* prior to randomization	1 minute before start of screening phase
Screening	00:00 of the date of signing the informed consent	1 minute before the first study medication intake
Treatment	Date time of first study medication intake	Date time of last investigational medication intake + 72 hours
Follow-up	End of Treatment phase + 1 minute	Trial termination date (date of last contact) with timestamp 23:59.

*In order to account for “approximately” 72 hours prior to randomization

The last phase, whichever it is for a subject, always ends on 23:59 of the day of trial termination (last contact) in study 64041575RSV2004. Note a subject can volunteer for long-term follow-up, in this case the subject will be enrolled in study 64041575RSV2002.

Assessments will be assigned to phases based on their date time, seconds will be ignored. If the day part of the start date of the assessment is present but the time part is missing, the assessment will be allocated as if it started at 00:00h on the day of the assessment (unless for Adverse Events see details in section 6.1.1). If the day part of the end date of the assessment is present but the time part is missing, no formal imputation will be done, but these rules will only be applied in order to be able to allocate assessments to phases. The assessment will be allocated as if it happened at 23:59h on the day of the assessment.

As subjects do not always adhere to the protocol visit schedule, the following rules are applied to assign actual visits to analysis visits. Listed below are the visit windows and the target days for each visit.

All visits (regardless the investigated parameter) will be allocated to analysis visits based on the day relative to the start of study medication:

Target Day	Analysis visit (numeric version)	Analysis visit	Day Interval
$-\infty$	-1	Screening	≤ 1 ¹
1	0	Baseline	≤ 1 ²
1	1	Day 1	[1] ³
2	2	Day 2	[2]
3	3	Day 3	[3]
4	4	Day 4	[4]
5	5	Day 5	[5]
6	6	Day 6	[6]
7	7	Day 7	[7,9]

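### SAP 4.4 adds the 72-hour treatment-phase tail to treatment duration, so the exposure table overstates time on drug by a constant 60 hours

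*SAP*

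**What the plan says.** SAP 4.4 has one exposure measure, treatment duration, defined as the date and time of last intake minus "date/time of first study drug intake + 72 hours". Its use is descriptive: "Descriptive statistics for treatment duration will be presented by treatment group". A note adds that "treatment interruptions will not be taken into account for the above definition".

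The same 72 hours appears in SAP 2.1, where the Treatment phase starts at first intake and ends at "Date time of last investigational medication intake + 72 hours". That phase is used to allocate adverse events and other assessments.

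On the regimen, SAP 4.3 states "The planned number of doses is 1 loading dose and 9 maintenance doses", with up to 19 maintenance doses if treatment is extended. Protocol 6 states "Subjects will be dosed with a single LD followed by 9 MDs twice daily (minimum 8 hours and maximum 16 hours apart", with at most two doses per calendar day, over Day 1 to Day 5/6. On length, Protocol 3.2 states "Treatment will last for 5 days as this was the duration of treatment assessed in healthy adult subjects infected with RSV". SAP 3.2 and Protocol 11.10 cap extended dosing at 10 days.

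**The concern.** A tail after the last dose is sensible when deciding which events belong to the treatment phase. It has no evident place in a measure of how long a child was treated, and SAP 4.4 gives no reason for it. The protocol uses the term treatment duration for the 5-day course and for its possible extension to 10 days. The SAP uses the same term for a quantity that cannot return 5 days for a complete course at nominal intervals.

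What is at stake is how the exposure table reads. A reader would take 7.5 days as time on drug, would see a child who took one dose as treated for 3 days, and could read a compliant extended course as running past the 10-day cap.

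**Working it through.** **Inputs**
- Doses planned: 1 + 9 = 10; if extended, 1 + 19 = 20 (SAP 4.3).
- Interval: twice daily, taken as 12 h; allowed gaps 8 to 16 h, at most two doses per calendar day (Protocol 6).
- Planned length: 5 days (Protocol 3.2); cap if extended: 10 days (SAP 3.2).
- Tail: 72 h (SAP 4.4, and SAP 2.1).

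**The protocol's own figure.** For n doses at 12-hour intervals, last minus first intake is (n − 1) × 12 h. Adding one dosing interval gives n × 12 h. For n = 10 this is 108 + 12 = 120 h = 5.0 days, which is the protocol's figure. For n = 20 it is 228 + 12 = 240 h = 10.0 days, which is the cap.

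**The SAP 4.4 rule:** (n − 1) × 12 + 72 h.

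| Doses | Last − first (h) | SAP 4.4: + 72 h | With + 12 h | Excess (h) | Ratio |
|---|---|---|---|---|---|
| 1 | 0 | 72 h (3.0 d) | 12 h (0.5 d) | 60 | 6.0 |
| 2 | 12 | 84 h (3.5 d) | 24 h (1.0 d) | 60 | 3.5 |
| 4 | 36 | 108 h (4.5 d) | 48 h (2.0 d) | 60 | 2.25 |
| 10 | 108 | 180 h (7.5 d) | 120 h (5.0 d) | 60 | 1.5 |
| 20 | 228 | 300 h (12.5 d) | 240 h (10.0 d) | 60 | 1.25 |

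**Range for a full 10-dose course under the allowed gaps.** The shortest span is about 88 h: two doses on each of Days 1 to 5, starting as late as an 8-hour gap allows on Day 1 and finishing as early as it allows on Day 5. The longest is about 144 h: nine gaps of just under 16 h, filling Days 1 to 6. SAP 4.4 then reports 88 + 72 = 160 h to 144 + 72 = 216 h, about 6.7 to 9.0 days. The 3 days for a single dose is exact, because no interval enters it.

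**Effect on comparisons.** The tail is the same for every child, so (mean₁ + 72) − (mean₂ + 72) = mean₁ − mean₂. The same holds for medians, and SDs do not change. Full course minus single dose is 180 − 72 = 108 h under SAP 4.4 and 120 − 12 = 108 h under the alternative. Only ratios move: a single dose is 72/180 = 40% of a full course under SAP 4.4, and 12/120 = 10% under the alternative.

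**Check on the reading of the formula.** Taken as last − (first + 72 h), it gives 36 h for a full course and −72 h for one dose. That cannot be meant, and it does not fit SAP 2.1.

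**Use of the term elsewhere in the SAP.** SAP 5.3.1.1 sets a viral load AUC window at 24 times the days with treatment, plus one day. With 5 days this is 24 × 5 + 24 = 144 h, the SAP's own AUC window to 144 h. With 7.5 days it would be 24 × 7.5 + 24 = 204 h. So the SAP appears to count the course as 5 days there.

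**The case against.** The strongest defence is that this is a stated definition and probably a deliberate one. It equals the length of the Treatment phase, so it describes the time window behind the by-phase safety tables. The drug also persists: Protocol 1.1.2 gives a plasma terminal half-life of about 63 h, and half-lives of the active triphosphate of 17.6 h in vitro and 29 h in monkey lung. Under a heading about exposure, a tail longer than 12 h is arguable.

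The first part stands as far as intent goes: nothing shows that the 72 h was copied by mistake. It does not rescue the label. Protocol 3.2 keeps the two ideas apart, expecting therapeutic triphosphate levels to continue after the 5-day treatment duration. Persistence is therefore additional to treatment duration in the protocol's own terms.

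It is also fair that the 12-hour rule is a convention that no document prescribes. Under the allowed gaps it gives 88 + 12 = 100 h to 144 + 12 = 156 h, or 4.2 to 6.5 days, so it returns exactly 5 days only at nominal intervals. That range reflects real variation in dosing times; the added 60 h does not.

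A reader might infer more: that the tail hides differences between arms in early stopping, or that children who stop early gain the most. The documents do not support this. The excess is constant, so it is largest in early stoppers only as a ratio, and SAP 4.4 plans no ratios. Early stopping is visible elsewhere by treatment group: discontinuations with reasons in SAP 4.2, doses taken over doses planned (loading and maintenance separately) in SAP 4.3, and adverse events leading to permanent stop in SAP 6.1.2. A child given only the loading dose shows 0% maintenance compliance.

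**Conclusion.** The point holds as a minor descriptive correction. SAP 4.4 labels the length of the treatment analysis phase as treatment duration, and so overstates time on drug by 60 h in every child relative to last minus first intake plus 12 h. At nominal intervals a full course reads 1.5 times the protocol's figure and an extended course 1.25 times the cap. A single dose reads 3 days at any interval.

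The 60 h rests on taking one nominal 12-hour dosing interval as the benchmark, which is the choice that reproduces the protocol's 5 and 10 days. No efficacy inference is affected: the primary analysis, alpha, power and the per-protocol rule do not use this variable. The adverse event summaries are percentages of subjects, with no exposure-adjusted rates planned.

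**What to change.** In SAP 4.4, define treatment duration as last intake − first intake + 12 hours (one nominal dosing interval). Leave the 72-hour tail in SAP 2.1, where it defines the end of the Treatment phase. Dose counts are already summarised as compliance in SAP 4.3, so no further exposure table is needed.

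The cost is one constant in the SAP and in the derivation program. No new data are needed, and no other analysis changes.

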4.5. Protocol Deviations

Only major protocol deviations will be defined in this trial. All major protocol deviations will be listed, including the deviations to the inclusion-exclusion criteria, and the violations to the prohibitions and restrictions, if any. A tabulation of the number and percentage of subjects per major protocol deviation will be provided

Note that the Per-protocol set definition takes into account any deviation from the protocol that could affect the efficacy. These are not necessarily major deviations, nor are major deviations considered to always affect efficacy and to warrant exclusion from the PP analysis.

4.6. Prior and Concomitant Medications

Prior and Concomitant medications will be summarized by preferred term using the World Health Organization Drug Dictionary (WHO-DD) as frequency tables in 2 parts:

1. Prior medication: medication that started before the first dose of study drug, regardless of when dosing of the medication ended
2. Concomitant medication: medication received at or after the first dose of study drug, medication that was received before initial dosing and continued after initial dosing of study drug, or medication with missing stop date.

(Medication that started before the first dose of study drug and continued after the first dose of study drug will be summarized as prior medication and separately as concomitant medication.)

The part on concomitant medication will be shown by ATC class level up to level 3.

If a prior/concomitant therapy record misses' components of its start and/or stop dates (time and/or day and/or month and/or year), the following actions will be taken:

1. In case of partial start or stop datetimes, the concomitant therapy records will be allocated to prior/concomitant using the available partial information, without imputations.
2. In case of a completely missing start date, the prior/concomitant therapy will be considered as having started before the trial.
3. In case of a completely missing end date, the prior/concomitant therapy will be considered as ongoing at the end of the trial.

Separate tables will be made for medication related to fever and not related to fever. Medication related to fever will be categorized as Acetaminophen/paracetamol, Ibuprofen, or other. These tables will be made by phase and combined phases and by treatment group and overall treatment.

4.7. Medical History

The medical history records will be listed; separate listings will be generated for conditions of interest (allergic/immunologic, dermatological)

5. EFFICACY

All efficacy will be analyzed on the Intention-To-Treat-infected (ITT-i) set.

5.1. Analysis Specifications

5.1.1. Level of Significance

Two contrasts will be tested at each of the interim analysis points and final analysis; a contrast with no difference between the 2 active regimens tested against placebo (high equal to low, better than placebo) and a contrast with a positive ‘linear’ dose-response relationship (high better than low, low better than placebo) with respect to active regimens (where the effect of the low dose is exactly in between that of placebo and the high dose regimen). With respect to multiple contrast testing, multiplicity (2 contrasts) will be controlled at the prespecified (interim) alpha level by calculating adjusted p-values from the simulated distribution of the maximum or maximum absolute value of a multivariate t random vector (ie, using the correlation between the contrasts to optimally control for alpha).

The significance level of *alpha* (α^*) will have to be calculated based on the information fraction at the time of the test using the pre-specified Pocock α spending function.

$$\alpha^*(t) = \alpha \cdot \ln(1 + (e-1) \cdot t)$$

where $t = n/N$, n is the ITT-i set size and N is the expected ITT-i set size at the end of study (=120).

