1.4. Sample Size Justification

On high dose, the hypothesis of the lumicitabine antiviral activity assumes a viral load reduction on the AUC of the log viral load over 7 days of at least 30% when compared to placebo in subjects with onset of symptoms ≤ 3 days and of at least 20% in subjects with onset of symptoms > 3 days. The antiviral activity on low dose is assumed to be 80% when compared to the antiviral activity on the high dose. The positive dose-response relationship assumes that dose regimens with higher exposure with respect to MD will have at least an equal or better effect on viral load. Therefore 2 contrasts will be tested at each of the interim analysis points and final analysis; a contrast with no difference between the 2 active regimens tested against placebo (high equal to low, better than placebo) and a contrast with a positive ‘linear’ dose-response relationship (high better than low, low better than placebo) with respect to active regimens (where the effect of the low dose is exactly in between that of placebo and the high dose regimen). With respect to multiple contrast testing, multiplicity (2 contrasts) will be controlled at the prespecified (interim) alpha level by calculating adjusted p-values from the simulated distribution of the maximum or maximum absolute value of a multivariate t random vector (ie, using the correlation between the contrasts to optimally control for alpha).

Based on the observed data of other in-house studies, the estimated SD is assumed to be approximately 34% of the AUC for subjects treated with placebo and the SD is equal in each of the treatment regimens. The overall (family wise) type 1 error rate of 2.5% (1-sided) will be adjusted for multiple testing due to formal interim analyses using a Pocock alpha spending function with 3 sequential tests (2 interim, 1 final). Based on 10,000 simulations and using a general linear model with treatment regimen as fixed factors, and under the assumption that 40% of the recruited subjects have onset of symptoms ≤ 3 days, a sample size of 180 subjects randomized in a 1:1:1 ratio will offer approximately 97% power to detect a positive dose-response relationship using multiple contrast testing. With the second interim analysis planned after at least 120 subjects, there will be at least 80% power to detect a positive dose-response relationship at the time of this analysis.

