The *lower* option is selected as the contrast needs to have a value below zero (ie, there needs to be a reduction in $AUC_{1-7\text{Days}}$ comparing active treatment to placebo). In summary, a positive dose-response relationship will be concluded if based on this analysis for any of the two estimations the resulting adjusted p-value is lower than the associated Pocock critical value (see section 5.1.1).

The differences in the $AUC_{1-7\text{Days}}$ for active versus placebo will be derived using appropriate contrasts deriving least square mean differences, including the 95% 2-sided confidence intervals.

The individual $AUC_{0-144\text{h}}$ as calculated using the trapezoidal rule will be considered as a supportive analysis and will be analyzed using a linear model with $AUC_{0-144\text{h}}$ as a dependent variable and treatment group and stratum as fixed factors, and baseline \log_{10} viral load as fixed covariate. For this analysis no adjustments for multiplicity will be applied, that is the differences versus placebo will be estimated using appropriate contrasts with 95% confidence intervals.

Before unblinding, the viral load data will be evaluated to assess whether viral load measurements based on swabs performed by the Health Care Provider (HCP) are similar as the swabs not performed by a HCP. Individual line plots will be created to visually check individual patterns for any difference between the samples. Depending on the visual inspection a decision will be made if all samples or only the samples from swabs performed by a HCP will be considered for the primary analysis. For example, if for the majority of subjects there is a clear drop in viral load when switched from samples taken by a HCP and samples taken by a non-HCP, the decision could be that only samples from swabs done by a HCP will be used. This blinded data review will be done before the database lock of the interim analysis and may also take other data sources into account.

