5.3.2.1. RSV RNA \log_{10} viral load qRT-PCR

Log₁₀ Viral Load

Descriptive statistics and mean (SE) graphs will be shown of the \log_{10} viral load actual values and changes from baseline. For exploratory purpose the \log_{10} viral load actual values and changes from baseline will also be shown by sampling method (measured in the mid-turbinate nasal swabs and endotracheal samples from intubated subjects).

Differences on RSV RNA \log_{10} viral load by qRT PCR between treatment groups and by analysis visit will be determined by using appropriate contrasts in the mixed model in which the primary endpoint is modelled. Nominal 95% confidence intervals will be used.

Peak viral load; Rate of decline

The Rate of decline of viral load over the first 24 hours will be analyzed using descriptive statistics including the geometric mean and the coefficient of variation (CV).

The log peak viral load and rate of decline of RSV RNA viral load will be compared for active groups versus placebo groups using a general linear model with treatment and strata included as fixed effects.

Residuals of the final model will be plotted in a normal probability plot.

In case the model does not fit the log peak value data well, the log transformation (ie. the log of log peak viral load) will be considered as dependent variable. The data from the model will be reported as (adjusted) differences in least squares (LS) means (in the case of untransformed data) or (adjusted) geometric mean ratios (in case of log-transformed data) of active dose groups versus placebo, including 95% confidence intervals using appropriate contrasts.

RSV viral load AUC's.

The same model used for the primary analysis will be used to test for a dose response relationship on the viral load AUC until Day 10, until Day 14 and until 1 day after last dose for subjects with treatment extension (if applicable) (respectively $AUC_{1-10Days}$, $AUC_{1-14Days}$ and $AUC_{1-xxDays}$). No corrections for multiplicity will be made, thus the significance level of alpha (α^*) will be kept at 0.05. The differences in these AUCs for active versus placebo will be derived using appropriate contrasts deriving least square mean differences, including the 95% 2 sided confidence intervals.

The sensitivity analysis will be similar as for the primary endpoint, using the calculated viral load AUCs per subject based on the trapezoidal method (AUC_{0-240h} , AUC_{0-336h} and AUC_{0-xxh}) as indicated in section 5.3.1.1.

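### SAP 5.1.1 uses the cumulative Pocock spending value as the level of each test, so after any interim superiority test the one-sided family-wise error exceeds 2.5%

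*SAP*

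**What the plan says.** SAP section 1.4 makes the commitment: "The overall (family wise) type 1 error rate of 2.5% (1-sided) will be adjusted for multiple testing due to formal interim analyses", by a Pocock spending function "with 3 sequential tests (2 interim, 1 final". Protocol section 11.2 says the same.

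SAP section 5.1.1 turns this into a rule. The significance level alpha* "will have to be calculated based on the information fraction at the time of the test using the pre-specified Pocock" function, alpha*(t) = alpha·ln(1+(e−1)t), with t = n/N, where "n is the ITT-i set size and N is the expected ITT-i set size at the end of study (=120".

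SAP section 5.2.3 places alpha* in the `alpha=` option of the primary code, next to the simulation adjustment for the two contrasts and the one-sided `lower` option. It concludes a positive dose-response if, for either contrast, "the resulting adjusted p-value is lower than the associated Pocock critical value (see section 5.1.1". Section 5.1.1 holds only the formula above.

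Superiority is a possible conclusion at both formal interims (SAP sections 1.2.1 and 3.1). The first is triggered by numbers in the symptom-duration strata. The second is at the sponsor's discretion.

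**The concern.** A spending function states how much type 1 error may have been used in total by information time t. To test at look k, one takes the increment since the previous look and solves for the boundary at which the chance of first crossing at look k equals that increment. The SAP has no such step. It labels the cumulative value as the level of the test and carries it into the code and the decision rule.

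At the first look the cumulative and incremental amounts are the same, so nothing goes wrong there. At any later look, error already spent is spent again. At t = 1 the formula returns the whole 0.025 whether or not an interim superiority test came before. What is at stake is the trial's one confirmatory error statement, on the primary endpoint.

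**Working it through.** **Inputs.** One-sided alpha 0.025, effect sizes, SD, onset mix, 180 subjects randomized 1:1:1 and 97% power come from SAP section 1.4. The formula and N = 120 come from section 5.1.1. The contrasts come from section 5.2.3. Per treatment arm (placebo, low, high) they are proportional to (−1, 0.5, 0.5) and (−1, 0, 1), so with equal arms their correlation is 1.5/√(1.5 × 2) = 0.866.

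**Assumptions.** The documents do not fix total look sizes. A first look at 90 follows from 36 subjects with onset ≤3 days at the assumed 40% share (36/0.40 = 90); 60 is tried as well. Information is proportional to n and allocation stays 1:1:1. Futility is non-binding, so it is ignored when counting type 1 error.

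**The plan's own figure.** The mean high-dose effect is 0.4 × 30% + 0.6 × 20% = 24%, and the low-dose effect is 0.8 × 24% = 19.2%, with SD 34%. Simulating 20,000 trials with looks at 90/120/180 and properly solved spending boundaries gives 96.4% cumulative power at 180 (stated: about 97%) and 84.2% at 120 (stated: at least 80%). Using alpha* as the level of each look gives 98.2% at 180, and a single test at 0.025 gives 97.8%. All are within 2 points of 97%, so the power statement cannot show which boundary was used.

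**Levels from the formula.**
- t = 0.5: 0.025 × ln(1.859) = 0.0155
- t = 2/3: 0.025 × ln(2.146) = 0.0191
- t = 0.75: 0.025 × ln(2.289) = 0.0207
- t = 1: 0.025 × ln(e) = 0.0250
- t = 180/120 = 1.5: 0.025 × ln(3.577) = 0.0319

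**Overall error.** Under the null, the two contrasts correlate 0.866 within a look, and each contrast correlates √(n_j/n_k) between looks j and k. The error is the probability that the larger of the two statistics crosses at any look.

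| Looks (total n) | N in formula | Level applied at each look | One-sided family-wise error |
|---|---|---|---|
| 90, 120 | 120 | 0.0207, 0.0250 | 3.4% |
| 60, 120 | 120 | 0.0155, 0.0250 | 3.4% |
| 90, 180 | 180 | 0.0155, 0.0250 | 3.4% (3.5% in one simulation) |
| 90, 120, 180 | 180 | 0.0155, 0.0191, 0.0250 | 4.0% |
| 90, 120, 180 | 120 | 0.0207, 0.0250, 0.0319 | 5.1% |

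**With the boundary solved.** For 90/120 and N = 120 the nominal adjusted-p levels are 0.0207 then 0.0118. For 60/120 and N = 120 they are 0.0155 then 0.0138. For 90/120/180 and N = 180 they are 0.0155, 0.0091 and 0.011. Each set returns an overall error of 2.5%.

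**The case against.** The intent looks standard. Section 5.1.1 calls the function a spending function, section 5.2.3 speaks of a critical value, section 1.4 promises control over three tests, and protocol section 11.2 cites a reference whose title concerns discrete sequential boundaries. A separate Interim Analysis Plan, not among the documents, may derive the boundaries. On this view the fault is an omitted step, not a wrong method.

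That is a fair account of intent, but it does not cure the text. The SAP's introduction says that it governs the final analysis. The final test is where the level is most clearly affected, and its only pointer is to the formula in 5.1.1. A programmer following the SAP would enter 0.025.

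Three limits do stand:
- The excess error is conditional. Up to two interims may be performed. With no formal superiority test before the end, 0.025 at n = N is correct. A reader might infer that error control is lost in every case; the documents do not support that.
- Levels of 0.0155, 0.0191 and 0.0250 are not what the SAP yields as it stands, because its N is 120. They apply only if N is set to 180.
- A reader might also infer that the dose-response tests on AUC to Day 10, Day 14 and end of extended treatment are twice as liberal as the primary. Section 5.3.2.1 says "No corrections for multiplicity will be made, thus the significance level of alpha" stays at 0.05, and it reuses the primary model, whose code is one-sided. But that section does not say one-sided, its next sentence gives two-sided 95% intervals, and no document sets 0.025 for these endpoints. They are secondary and cannot affect the primary error. This supports a request for clarification only.

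**Conclusion.** The point holds in conditional form. Followed literally, the primary decision rule does not deliver the promised 2.5% once at least one interim superiority test has been made. The error is about 3.4% with one interim and a final size equal to N, about 4.0% with two interims and N = 180, and about 5.1% with two interims when 180 are analysed and N is left at 120. The exact values depend on the assumed look sizes and 1:1:1 allocation, but every scenario tried with an interim exceeds 2.5%. Because this is the primary decision rule, it should be corrected before any formal superiority test.

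**What to change.** In SAP section 5.1.1, and consistently in the Interim Analysis Plan:
- State that alpha*(t) is the cumulative error to be spent, with alpha = 0.025 one-sided.
- Cap t at 1, set t = 1 at the final analysis, and reconcile N = 120 with the planned final size. Without this, spending at n = 180 would still reach 0.0319.
- Define the nominal level at look k as the value for which the probability of first crossing at look k equals alpha*(t_k) − alpha*(t_{k−1}), using the joint distribution over looks and the two contrasts.

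In section 5.2.3, use that nominal level both in `alpha=` and in the decision rule.

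As a minor clarification, state in section 5.3.2.1 whether the 0.05 level for the later AUC tests is one- or two-sided, and whether the `lower` option applies.

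The cost is SAP wording and a short boundary program. Under the section 1.4 assumptions, power at 180 is 96.4% with solved boundaries, against 98.2% under the literal rule and about 97% stated.
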